5.1.2.1 Other imputations

Incomplete date of initial diagnosis of cancer

Missing day is defaulted to the 15th of the month and missing month and day is defaulted to 01-Jan.

5.2 AEs coding/grading

Adverse events are coded using the latest available version of Medical dictionary for regulatory activities (MedDRA) terminology.

AEs will be assessed according to the Common Terminology Criteria for Adverse Events (CTCAE) version 5.0.

The CTCAE represents a comprehensive grading system for reporting the acute and late effects of cancer treatments. CTCAE grading is by definition a 5-point scale generally corresponding to mild, moderate, severe, life threatening, and death. This grading system inherently places a value on the importance of an event, although there is not necessarily proportionality among grades (a grade 2 is not necessarily twice as bad as a grade 1).

5.3 Laboratory parameters derivations

Grade categorization of lab values will be assigned programmatically as per NCI Common Terminology Criteria for Adverse Events (CTCAE) version 5. The calculation of CTCAE grades will be based on the observed laboratory values only, clinical assessments will not be taken into account. The criteria to assign CTCAE grades are given in Novartis internal criteria for CTCAE grading of laboratory parameters (embedded below). The latest available version of the document based on the underlying CTCAE version v5 at the time of analysis will be used. For laboratory tests where grades are not defined by CTCAE v5, results will be graded by the low/normal/high (or other project-specific ranges, if more suitable) classifications based on laboratory normal ranges.

A severity grade of 0 will be assigned for all non-missing lab values not graded as 1 or higher. Grade 5 will not be used. For laboratory tests that are graded for both low and high values, summaries will be done separately and labelled by direction, e.g., sodium will be summarized as hyponatremia and hypernatremia.

EASE LAB - CTC
grades in Novartis Or

Imputation Rules

Hematology

Immature cells (promyelocytes, myelocytes, metamyelocytes and blasts) will not be displayed in shift tables and will only be listed.

Immature cells are manually counted only if anomalies are detected during the automatic testing. Therefore, when the automatic testing was performed but no data is transferred for immature cells, this means there was no immature cells and their values can be imputed to 0. Note that there should not be any imputation in case the automatic testing was not performed or the test of immature cells is present with missing value in the database (this would mean the test was to be performed but couldn't).

CTCAE grading for blood differentials is based on absolute values. However, this data may not be reported as absolute counts but rather as percentage of white blood cells (WBC).

If laboratory values are provided as '<X' (i.e. below limit of detection) or '>X', prior to conversion of laboratory values to SI unit, these numeric values are set to X.

The following rules will be applied to derive the WBC differential counts when only percentages are available for a certain differential

$$\text{Differential count} = (\text{WBC count}) * (\% \text{value} / 100)$$

The following rules will be applied to derive the WBC differential percentages when only differential counts are available for a certain differential

$$\% \text{value} = (\text{differential count} \times 100) / \text{WBC count}$$

Further derivation of laboratory parameters might be required for CTCAE grading. For instance, corrected calcium can be derived using the reported total calcium value and albumin at the same assessment using the following formula:

$$\text{Corrected Calcium (mmol/L)} = \text{Calcium (mmol/L)} + 0.02 (40 - [\text{Albumin (g/L)}])$$

For calculation of laboratory CTCAE grades 0 and 1, the normal range for derived corrected calcium is set to the same limits (in mmol/L) as for calcium.

CTCAE grades for the derived absolute WBC differential counts (neutrophils, lymphocytes) and corrected calcium will be assigned as described above for grading.

5.4 Efficacy variables

5.4.1 Molecular response

Scaling towards an international standard will be performed for all molecular results using laboratory specific conversion factors. In this process, the raw ratio between BCR::ABL and the control gene ABL is calculated and multiplied by the lab-specific conversion factor ([[Branford and Hughes 2006](#)]). Therefore, using the international unit, the BCR::ABL ratio will be presented in %. The MRDx assay using PAXgene™ Blood RNA tubes from MMD laboratory will be used in this study. The lab conversion factor for this assay was 1.1 until 1 June 2020 and 1 thereafter.

The BCR::ABL ratio in IS % is calculated by multiplying the raw BCR::ABL ratio with the lab-specific conversion factor and then by 100:

$$\text{BCR::ABL ratio (in \%)} = (\text{BCR::ABL} / \text{ABL}) * \text{conversion factor} * 100$$

The BCR::ABL ratio in IS% provided by the central laboratory will be use in the analyses. However, to calculate the fold change in BCR::ABL1/ABL used to derive the loss of MMR criteria, in case the BCR::ABL number of copies is reported as a 0 value and the subject doesn't have atypical transcript at baseline, then the value will be replaced by 1, and the BCR::ABL ratio will be calculated.

Molecular response is categorized as follows:

- 10% > BCR::ABL ratio
- 1% < BCR::ABL ratio ≤ 10%
- 0.1% < BCR::ABL ratio ≤ 1%
- 0.01% < BCR::ABL ratio ≤ 0.1%
- 0.0032% < BCR::ABL ratio ≤ 0.01%
- BCR::ABL ratio ≤ 0.0032%

If the BCR::ABL number of copies or BCR::ABL ratio is reported as “Not Detected”, then the BCR::ABL ratio will be imputed to 0.

Levels of BCR::ABL1 transcripts will be determined by real-time quantitative PCR (RQ-PCR) testing of peripheral blood and analyzed centrally. Log reduction in BCR::ABL1 transcripts levels from the standardized baseline value, or the percent ratio of BCR::ABL1 transcripts versus control gene (ABL1) transcripts converted to a reference standard, international scale (IS) ([Hughes and Branford 2006](#)), will be calculated for each sample.

Major molecular response and related variables are defined as the following:

- Rate of MMR where MMR is defined as a ≥ 3.0 log reduction in BCR::ABL1 transcripts compared to the standardized baseline equivalent to ≤ 0.1 % BCR::ABL1/ABL1 % by IS as measured by RQ-PCR, confirmed by duplicate analysis of the same sample,
- Time to MMR defined as the time from the date of randomization to the date of the first documented MMR,

- Duration of MMR defined as the time from the date of first documented MMR to the earliest date of loss of MMR, progression to AP or BC, or CML-related death.
- Rate of Deep Molecular Responses MR4 and MR4.5 are defined as a ≥ 4 log or ≥ 4.5 log reduction in BCR::ABL1 transcripts compared to the standard baseline equivalent to 0.01 % or 0.0032% BCR::ABL1/ABL by IS as measured by RQ-PCR, confirmed by duplicate analysis of the same sample with at least 10,000 or 32,000 ABL1 transcripts, respectively.

Loss of MMR is defined as increase of BCR::ABL1/ABL to $> 0.1\%$ by international scale (IS) in association with a ≥ 5 -fold rise in BCR::ABL1 from the lowest value achieved on study treatment and replicated by a second analysis of the same sample. Confirmed loss of MMR by subsequent sample analysis within 4 to 6 weeks showing loss of MMR associated with a ≥ 5 -fold rise in BCR::ABL1 from the lowest value achieved on study treatment, unless it is associated with confirmed loss of CHR or loss of CCyR or progression to AP/BC or CML-related death.

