2.6.2 Statistical hypothesis, model, and method of analysis

No statistical testing of secondary efficacy endpoints will be performed .

Molecular response at and by time points

- Molecular Response MMR rate at weeks 12, 24, 36, 72, 96 and 144
- MMR rate at week 48 for subjects with MMR at baseline
- Rate of MR4 and MR4.5 at weeks 12, 24, 36, 48, 72, 96 and 144
- Rate of BCR::ABL1 $\leq 10\%$ and $\leq 1\%$ at Weeks 12, 24, 36 and 48
- Rate of BCR::ABL1 $\leq 10\%$, BCR::ABL1 $\leq 1\%$, MMR, MR4 and MR4.5 by all-time points

Frequency and percentage of all molecular response categories (defined in [Appendix](#)) using FAS or FAS 2 will be presented for each time point.

For each endpoint above, the rate and the associated 95% confidence interval based on the Clopper-Pearson method will be presented. For the at-time-points summary, subjects discontinuing the treatment prior to a specific time point due to any reason or subjects without an available assessment at that time point will be considered as non-responders for that time point. For the by-time-points summary, subjects without any documented response for which an evaluable response assessment was never provided will be considered as non-responders for the period of time up to that time point.

The cumulative incidence of MMR will be graphically displayed by an increasing step function. This curve will increase each time (after randomization) at which a new responder is observed and thus will increase up to the best observed response rate (e.g. up to 50% if half of the subjects in the analysis population are able to achieve response).

Additional chromosomal abnormalities and occurrence of high-risk ACAs

The number and percentage of subjects achieving MMR at week 48 and week 96, and CCyR at week 48 will be presented by ACA status at baseline. Per NCCN 2024 guideline and ELN 2020 guideline, the major route ACA/Ph+ including trisomy 8, isochromosome 17q, second Ph, trisomy 19, and chromosome 3 abnormalities are considered as presence of ACA at baseline.

Time to MMR

Time to MMR is defined in protocol Section 8.3.1.1 and calculated as: date of first documented MMR - date of randomization +1. Descriptive statistics (minimum, maximum, median, quartiles, mean, SD) of time to MMR will be provided.

The FAS will be also used to perform similar Time-to-Event analyses as described below for duration of MMR.

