5.5 Derivation of response rates and categories

5.5.1 Response rate at a specific time point

The molecular and cytogenetic response evaluations will be summarized by the following mutually exclusive categories which are based on the respective assessment within the time window:

- **Response categories** (sections 5.4.1 and 5.4.2): Subjects with an available assessment at that time point (+/- time window) indicating any of the response categories.
- **No response:** Subjects with assessment at that time point (+/- time window) indicating 'no response'
- **Missing:** Subjects without an evaluable response assessment at that time point (+/- time window). This category is then further split into subjects who are ongoing without treatment failure at the beginning of the relevant time window, subjects who are ongoing with treatment failure at the beginning of the relevant time window, subjects who discontinued due to lack of efficacy, disease progression (PD) or death and subjects who discontinued due to other reasons.

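### SAP 5.4.1 molecular response categories: the first row is reversed, and not-detected samples enter the deepest row whatever their ABL1 count

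*SAP*

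**What the plan says.** SAP 5.4.1 lists six categories of the BCR::ABL ratio on the International Scale. The first is "10% > BCR::ABL ratio" and the second is "1% < BCR::ABL ratio ≤ 10"%. The list continues down to "0.0032% < BCR::ABL ratio ≤ 0.01"% and "BCR::ABL ratio ≤ 0.0032"%. All six rows are defined by the ratio alone.

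For a result reported as not detected, "then the BCR::ABL ratio will be imputed to 0". No ABL1 count is attached to that rule. Further on, the same section defines MR4 (0.01%) and MR4.5 (0.0032%) as "confirmed by duplicate analysis of the same sample with at least 10,000 or 32,000 ABL1 transcripts, respectively".

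The list is put to use. SAP 2.6.2 calls for "Frequency and percentage of all molecular response categories" at each time point on the FAS or FAS 2, under the same heading as the MR4 and MR4.5 rates. SAP 5.5.1 says the response evaluations will be summarised by "mutually exclusive categories which are based on the respective assessment within the time window" and refers back to 5.4.1 for them.

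**The concern.** A programmer works from this text. Followed as written, the first row collects nearly everyone, and patients with the poorest response have no row of their own.

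The second problem would survive correction of the first. The two deepest rows are cut at exactly the MR4 and MR4.5 thresholds, so a reader will take them as MR4 and MR4.5. They lack the sensitivity condition that the SAP attaches to those terms. If a sample contains few ABL1 transcripts, failing to find BCR::ABL says little about how deep the response is, yet the imputation to 0 sends it to the deepest row. The report could then show more patients at ≤ 0.0032% than in MR4.5, with no rule explaining the gap. Any such error runs towards deeper response.

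**Working it through.** **Inputs, all from SAP 5.4.1 unless noted.** The six rows as printed. Ratio (%) = (BCR::ABL copies / ABL copies) × conversion factor × 100, with factor 1 after 1 June 2020. Not detected becomes 0. Minimum ABL1 transcripts: 10,000 for MR4 and 32,000 for MR4.5. Mutual exclusivity comes from 5.5.1.

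**The plan's own thresholds.** One copy in 10,000 is 1/10,000 × 100 = 0.01%. One copy in 32,000 is 1/32,000 × 100 = 0.003125%, just under 0.0032%. The two minimums are therefore about the counts at which a single copy would sit at the MR4 and MR4.5 limits, so the definitions are coherent.

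**Step 1: assign test ratios to the rows.**

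| Ratio | Rows as printed | With first row as ratio > 10% |
|---|---|---|
| 50% | none | > 10% |
| 15% | none | > 10% |
| 10% | 1–10% | 1–10% |
| 5% | < 10% and 1–10% | 1–10% |
| 0.5% | < 10% and 0.1–1% | 0.1–1% |
| 0.05% | < 10% and 0.01–0.1% | 0.01–0.1% |
| 0.005% | < 10% and 0.0032–0.01% | 0.0032–0.01% |
| 0 | < 10% and ≤ 0.0032% | ≤ 0.0032% |

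As printed, the list is neither exhaustive nor mutually exclusive. Reversing the one sign puts every ratio in exactly one row.

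**Step 2: not-detected samples, with the first row corrected.** One-copy ratio = 100 / ABL1 count, in %.

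| ABL1 copies | One copy would be | Row for not detected | MR4 minimum met | MR4.5 minimum met |
|---|---|---|---|---|
| 5,000 | 0.02% | ≤ 0.0032% | no | no |
| 9,999 | 0.010001% | ≤ 0.0032% | no | no |
| 12,000 | 0.0083% | ≤ 0.0032% | yes | no |
| 20,000 | 0.005% | ≤ 0.0032% | yes | no |
| 32,000 | 0.003125% | ≤ 0.0032% | yes | yes |

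The row never changes, while the status under the MR definitions does.

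**Step 3: the gap between table and rates.** Assume whole copies and conversion factor 1, and set aside the duplicate-analysis requirement. At one visit, let *a* be the number of not-detected samples below 10,000 ABL1 copies and *b* the number with at least 10,000 but fewer than 32,000. Let *c* be the number of samples with one detected copy and at least 31,250 (100/0.0032) but fewer than 32,000 ABL1 copies; these have a ratio of at most 0.0032% but miss the MR4.5 minimum. Then:

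- count in the deepest row − MR4.5 count = *a* + *b* + *c*
- count in the two deepest rows together − MR4 count = *a*

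The 0.0032–0.01% row admits no under-sized samples. Not-detected results never enter it, and a detected copy in fewer than 10,000 ABL1 gives more than 0.01% (1/9,999 = 0.010001%). The route is essentially *a* and *b*; *c* covers a very narrow band.

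**Step 4: can *a* and *b* be sized?** No. Neither document gives the distribution of ABL1 counts. Protocol 8.3.1.1 asks for another sample when a result is hard to interpret or not analysable, but states no copy threshold.

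**The case against.** The reversed sign is plainly a slip. The next row and the exclusivity rule leave one sensible reading, and the ≤ 10% and ≤ 1% endpoints are stated separately and correctly. SAP 5.5.1 also has a 'no response' line that might catch ratios above 10%. Most of this stands, but that line is not defined for molecular response and would not cure the double counting below 10%.

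The rows are labelled by ratio, not as MR4 or MR4.5, so a ratio table may legitimately differ from copy-qualified rates. This also stands, provided the table says so; at present it does not.

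Several stronger inferences should be resisted:

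- **Deep-response rates or the treatment-free-remission objective are biased.** The MR4 and MR4.5 rates carry the copy minimums in their own definitions. The treatment-free-remission objective is measured by duration of MR4 without loss of MMR. Neither is derived from this table.
- **The missing > 10% row interferes with the mandatory stop in protocol 9.1.1.** That rule acts on a patient's own result, not on a summary row.
- **The deepest row is inflated by some stated percentage.** Nothing in the documents supports a figure.
- **A low-copy sample fixes a patient in the deepest row for all later visits of the by-time-point table.** That would follow if the table takes the best category to date. SAP 2.6.1.1 spells out a cumulative rule only for MMR and is less explicit for the categories.

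**Conclusion.** Both errors are in the SAP text and should be corrected. The first makes the category list unusable if taken literally, although the intended meaning is clear. The second is a real mismatch between the deepest row and the MR4.5 definition in the same section. The excess in that row lies anywhere from none, if every not-detected sample has at least 32,000 ABL1 copies, to all of the not-detected samples, if none does, plus the rare single-copy case.

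The consequence is limited to the supporting category tables. The primary MMR endpoint at week 48 uses ≤ 0.1% and depends on neither point. The step 3 arithmetic assumes whole copies and a conversion factor of 1; the mismatch for not-detected samples needs neither assumption.

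**What to change.** In SAP 5.4.1, print the first row as BCR::ABL ratio > 10%. Then replace the three deepest ratio rows with response categories:

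- MR4.5: ratio ≤ 0.0032% and ABL1 ≥ 32,000.
- MR4 but not MR4.5: ratio ≤ 0.01%, ABL1 ≥ 10,000, and MR4.5 not met.
- MMR but not MR4: ratio ≤ 0.1% and MR4 not met.

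Assign each not-detected sample to the deepest of these that its ABL1 count supports. Relabelling is needed as well as the copy condition. Otherwise a not-detected sample with 12,000 copies would carry an imputed ratio of 0 in a row headed 0.0032–0.01%. Because the SAP's MMR definition has no copy minimum, a not-detected sample below 10,000 copies goes to MMR but not MR4, and the rows then add up to the MMR, MR4 and MR4.5 counts.

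If the sponsor prefers to keep a ratio table, the minimum is the corrected first row and a footnote that the rows are ratio-only and not equivalent to MR4 or MR4.5.

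The cost is SAP wording and one derivation from ABL1 counts already needed for the MR4 and MR4.5 rates; no new data are required. The visible effect may be fewer patients in the deepest row.

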Study treatment	
The investigational treatment for this study is asciminib (80 mg daily, randomized to either 40 mg b.i.d. or 80mg q.d.). In patients not achieving MMR at 48 weeks or losing the response after the week 48 assessment up to week 108, asciminib dose may be escalated to 200 mg q.d. per investigator decision. Novartis will supply asciminib to the investigational site as 20 mg and 40 mg tablets.

Treatment of interest	
Asciminib

Efficacy assessments	
 • The efficacy of asciminib will be primarily assessed through molecular monitoring by Real Time Quantitative Polymerase Chain Reaction (RQ-PCR) of the BCR-ABL1 transcripts in the peripheral blood, the standard methodology for assessing CML disease activity. RQ-PCR assessments will be performed at each study visit (except at Week 1 Day 1, Week 2 Day 1, Week 4 and Week 8 visits). For patients who escalate

	
dose an additional, 2-week post-escalation ECG visit will be performed, there will be no RQ-PCR assessment done for this visit.
 
 • At selected visits cytogenetic analyses will be performed locally to assess the number of Philadelphia-positive cells in the bone marrow and additional cytogenetic aberrations. Cytogenetic analysis is a second standard assessment of disease status and response to treatment in CML. • Additional routine assessments of cell counts in peripheral blood will be performed at every visit. Though these are less sensitive than molecular monitoring and cytogenetics, an increase in blast cells may indicate a lack of response and potential sign of disease progression.
Key safety assessments	
 • Adverse event monitoring • Physical examination • Vital Signs • Hematology and biochemistry (and pregnancy when applicable) • 12-lead Electrocardiogram (ECG)
Other assessments	
 • Patient Reported Outcomes: MD Anderson Symptom Inventory – Chronic Myelogenous Leukemia (MDASI-CML) • Biomarker assessments (BCR-ABL1 resistance mutation analysis for ATP binding site and myristoyl binding site mutations) • CCI

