Patients who are intolerant to ongoing TKI treatment but in MMR will also be allowed to enter the trial. Management of side effects represent a significant challenge with TKIs, in particular as patients may achieve a normal life expectancy. Data from ASCEMBL ([Hochhaus et al 2020c](#)) support a more favorable safety profile of asciminib compared with bosutinib. Patients with long-lasting side effects may therefore benefit from a switch to asciminib and an improved quality of life, while at the same time have little risk of losing the previously attained good response. All patients will also be closely monitored so any loss of molecular response will be detected early.

The patient selection in this protocol is based on the ASCEMBL study, while expanding on the latest finding and results from this trial to reflect the optimum in safety management. Efficacy of the drug is assessed through molecular monitoring in central lab standardized to the international scale. With the exception of the bone marrow assessment required for response

monitoring, the protocol does not include invasive examination. Patient visits are aligned with the safety monitoring requirements as well as with current treatment recommendations and represent a common schedule that is also required in clinical practice outside of the study. It is therefore anticipated, that the protocol will take every precaution to allow for the best possible safety of the patients while at the same time carefully managing the additional burden of the trial to patients.

Patients will be randomized 1:1 into two treatment groups treated with asciminib 40 mg b.i.d or 80 mg q.d. Based on the available clinical data as well as the extensive exposure-efficacy and efficacy-safety analyses, the risk/benefit ratio of asciminib administered at 80 mg q.d. in patients with CML not harboring the T315I mutation is not different than that of asciminib 40 mg b.i.d.

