8.3.1.1 Molecular response

Molecular response (MR) will be assessed in all patients.

Levels of BCR-ABL1 transcripts will be determined by real-time quantitative PCR (RQ-PCR) testing of peripheral blood and analyzed centrally. Log reduction in BCR- ABL1 transcripts levels from the standardized baseline value, or the percent ratio of BCR-ABL1 transcripts versus control gene (ABL1) transcripts converted to a reference standard, international scale (IS) ([Hughes and Branford 2006](#)), will be calculated for each sample.

Major molecular response and related variables are defined as the following:

- Rate of MMR where MMR is defined as a ≥ 3.0 log reduction in BCR-ABL1 transcripts compared to the standardized baseline equivalent to ≤ 0.1 % BCR-ABL1/ABL1 % by IS as measured by RQ-PCR, confirmed by duplicate analysis of the same sample,
- Time to MMR defined as the time from the date of enrollment to the date of the first documented MMR,
- Duration of MMR defined as the time from the date of first documented MMR to the earliest date of loss of MMR, progression to AP or BC, or CML-related death.
- Rate of Deep Molecular Responses MR4 and MR4.5 are defined as a ≥ 4 log or ≥ 4.5 log reduction in BCR-ABL1 transcripts compared to the standard baseline equivalent to 0.01 % or 0.0032% BCR-ABL1/ABL by IS as measured by RQ-PCR, confirmed by duplicate analysis of the same sample with at least 10,000 or 32,000 ABL1 transcripts, respectively.

Loss of MMR is defined as increase of BCR-ABL1/ABL to $> 0.1\%$ by international scale (IS) in association with a ≥ 5 -fold rise in BCR-ABL1 from the lowest value achieved on study

treatment and replicated by a second analysis of the same sample. Loss of MMR confirmed by subsequent sample analysis within 4 to 6 weeks showing loss of MMR associated with a ≥ 5 -fold rise in BCR-ABL1 from the lowest value achieved on study treatment, unless it is associated with confirmed loss of CHR or loss of CCyR or progression to AP/BC or CML-related death. The blood samples will be taken as described in [Table 8-1](#) and [Table 8-2](#).

If at one visit the sample is missing during transit to the central PCR laboratory, or the PCR result is difficult to interpret or sample not analyzable, or if the PCR sample was not collected, a subsequent unscheduled visit sample must be collected within 4 weeks either at the next scheduled visit (week 4 or week 8) or as an unscheduled visit.

Table 8-2 Blood samples (efficacy primary endpoint)

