The reference start date for safety assessments (e.g. adverse event onset, laboratory abnormality occurrence, vital sign measurement, dose interruption, etc.) is the start of study treatment.

The reference start date for all other, non-safety assessments (e.g. molecular response, disease progression, ECOG performance status, patient reported outcomes (PRO), etc.) is the date of randomization.

The reference start date for dose escalation (200 mg q.d.) is the date when a subject starts first escalated dose.

The study day will be displayed in the data listings. If an event starts before the reference start date, the study day displayed on the listing will be negative.

Time unit

A year length is defined as 365.25 days. A month length is 30.4375 (=365.25/12) days. If duration is reported in months, duration in days will be divided by 30.4375. If duration is reported in years, duration in days will be divided by 365.25.

A week length is defined as 7 days. If duration is reported in weeks, duration in days will be divided by 7.

Baseline for the treatment period

For efficacy evaluations, the last non-missing assessment, including unscheduled assessments on or before the date of randomization is taken as “baseline” value or “baseline” assessment. In the context of baseline definition, the efficacy evaluations also include PRO and performance status.

For safety evaluations, the last available assessment, including unscheduled assessments before the date of start of study treatment is taken as “baseline” assessment.

For pre-dose electrocardiogram (ECG), the last available assessment before the treatment start date is used for baseline.

For ECGs requiring triplicate measures per time point, the average of these measurements will be reported by sites in eCRF baseline.

For mutations, the screening/baseline assessment is taken as “baseline” assessment.

In rare cases where multiple laboratory measurements meet the baseline definition, with no further flag or label that can identify the chronological order, then the following rule should be applied: If values are from central and local laboratories, the value from central assessment should be considered as baseline.

If subjects have no value as defined above, the baseline result will be missing.

On-treatment assessment/event and observation periods

For adverse event reporting the overall observation period will be divided into three mutually exclusive segments:

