For subjects in the FAS who have not experienced any MMR, the time will be censored as follows in the Kaplan-Meier analysis:

- If a subject does not achieve the specified response before the cut-off date for the analysis, censoring time will be the last molecular assessment (PCR) date on treatment prior to the cut-off date or the EoT visit, whichever comes first.
- If a subject discontinues study treatment prior to achieving a response for a reason other than disease progression or death, then the subject will be censored at the last molecular assessment (PCR) date on treatment prior to the cut-off date or the EoT visit, whichever comes first.
- If a subject discontinues study treatment prior to achieving a response due to progression or death, then the censoring time will be set to the longest follow-up time in the treatment group, that is, consider the response is impossible to reach.
- In case no on-treatment response assessment was performed, the subject will be censored at day 1.

The estimated cumulative incidence rates and 95% confidence intervals at 12, 24, 48, 72, 96 and 144 weeks will be presented. The cumulative incidence curve will be plotted.

Duration of MMR

Duration of MMR is defined in protocol Section 8.3.1.1 as the time from the date of first documented MMR to the earliest date of confirmed loss of MMR, progression to AP or BC, or CML-related death. The time will be censored at the last molecular assessment (PCR) date while on treatment for subjects who have not experienced any of the above events. The duration of MMR will be analyzed for the subjects in FAS who achieve MMR at any time.

Duration of MMR will be analyzed by K-M method and presented by K-M plots. The survival distribution of duration of MMR will be estimated using the Kaplan-Meier method, and Kaplan-Meier curves, medians and 95% confidence intervals [[Brookmeyer and Crowley 1982](#)] of the medians, along with the proportion of subjects who are still in MMR at 24, 48, 72, 96 and 144 weeks and the associated 95% confidence intervals, will be presented.

Duration of MR4 without loss of MMR will be analyzed in a similar fashion to the analysis of duration of MMR.

The additional subjects who were intolerant to the last TKI and were in MMR already at baseline will be assessed for the duration of MMR using FAS 2.

CCyR rates at time points

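### For patients already in MMR at baseline (FAS 2), the loss-of-MMR rule ignores the baseline value, so an early loss can be missed or dated late and duration of MMR can be overstated

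*SAP*

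**What the plan says.** Protocol 8.3.1.1 and SAP 5.4.1 share one definition of loss of MMR, with two limbs: a value above 0.1% IS, and at least a 5-fold rise "from the lowest value achieved on study treatment and replicated by a second analysis of the same sample". The protocol sets the same reference ("rise in BCR-ABL1 from the lowest value achieved on study" treatment). Confirmation by a later sample, 4 to 6 weeks on, is judged against the same nadir.

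Baseline lies outside that reference. Under SAP 2.1.1, for efficacy, "the last non-missing assessment, including unscheduled assessments on or before the date of randomization is taken as" the baseline value. Protocol Table 8-2 schedules the next RQ-PCR sample at Week 12. The only stated adjustment to the fold change (SAP 5.4.1) replaces a zero copy number by 1.

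Duration of MMR runs from first documented MMR to confirmed loss, progression to AP/BC or CML-related death. Patients without an event are censored at their last on-treatment PCR. SAP 2.6.2 extends this to the patients who "were in MMR already at baseline will be assessed for the duration of MMR using FAS 2", and gives them no separate reference value or time origin. Duration of MR4 without loss of MMR is to be analysed in the same way.

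**The concern.** The rule suits patients who first reach MMR on study: their on-treatment nadir is at or below 0.1% by the time duration starts to run. FAS 2 patients bring their response with them. If it is lost soon after the switch to asciminib, the on-treatment nadir may already be a raised value, and the 5-fold limb is then measured from that value.

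Duration of MMR is a stated secondary objective for this cohort (SAP Table 1-1 and 2.6). Protocol 4.5 justifies enrolling these patients by a low expected risk of losing their response, and adds: "All patients will also be closely monitored so any loss of molecular response will be detected early". That sentence concerns clinical monitoring, which the analysis rule does not alter. It does show that an early loss after the switch is the outcome of most interest, and that is the loss the duration curve is least able to register. The same patient, at 0.3% throughout, would be a Week 48 non-responder and yet event-free in the duration analysis.

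**Working it through.** The documents give no figure for duration of MMR in FAS 2, so there is none to reproduce. The check applies the rule as written to illustrative PCR series.

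**Inputs**
- Absolute limb: above 0.1% IS (SAP 5.4.1).
- Relative limb: at least 5 × R, where R is the lowest on-treatment value (SAP 5.4.1, Protocol 8.3.1.1).
- First scheduled on-treatment PCR: Week 12 (Protocol Table 8-2).
- Cohort size: up to 30 (Protocol Section 5).
- Assumed: the PCR series below, confirmation met, and no unscheduled PCR before Week 12.

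**Formula.** Loss at visit t requires v(t) > 0.1% and v(t) ≥ 5 × R(t), with R(t) the minimum of the on-treatment values up to t.

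**Step 1, Week 12.** R = v(12), so v(12)/R = 1. The 5-fold limb fails whatever the value.

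**Step 2, later visits.** If Week 12 is the nadir, loss is declared only at 5 times it: 5 × 0.15% = 0.75%; 5 × 0.3% = 1.5%; 5 × 0.5% = 2.5%.

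**Step 3, who is exposed.** 0.1% / 5 = 0.02%. With any earlier on-treatment value at or below 0.02%, every value above 0.1% is already at least a 5-fold rise and nothing is masked. Exposure needs all earlier on-treatment values to exceed 0.02%.

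**Step 4, rule as written against a reference that includes baseline** (% IS, Weeks 12, 24, 36, 48, 60):

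| Baseline | On-treatment values | Loss as written | Loss with baseline in reference |
|---|---|---|---|
| 0.01 | 0.5 throughout | none | Week 12 |
| 0.05 | 0.3, 0.6, 0.9, 1.2, 1.2 | none | Week 12 |
| 0.02 | 0.2, 0.6, 1.0, 1.0, 1.0 | Week 36 | Week 12 |
| 0.005 | 0.08, 0.3, 0.35, 0.39, 0.39 | none | Week 24 |
| 0.05 | 0.02, 0.15, 0.2, 0.2, 0.2 | Week 24 | Week 24 |
| 0.08 | 0.3 throughout | none | none |

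In the fourth row, Week 24 is 0.3/0.005 = 60-fold above baseline but 0.3/0.08 = 3.75-fold above the nadir, and the highest value reaches only 0.39/0.08 = 4.9-fold. In the last row, 0.3/0.08 = 3.75-fold falls short under either reference.

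**Step 5, direction.** The lower of baseline and nadir is never above the nadir. A loss counted as written is therefore never dated earlier than one counted with baseline included.

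**Step 6, size.** One patient in 30 is 1/30 = 3.3 points, and more if fewer are at risk. With k masked Week 12 losses among 30, and no other event or earlier censoring, the curve reads 100% as written. With baseline in the reference it reads (30 − k)/30: 96.7% for k = 1, 90.0% for k = 3, 80.0% for k = 6. The values of k are assumed; k = 0 gives no difference.

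**Step 7, MR4.** If MR4 is documented on treatment, R ≤ 0.01% and 5 × 0.01% = 0.05%, below the 0.1% limb. Any value above 0.1% is then more than a 10-fold rise and is counted. Masking needs MR4 at baseline that is never seen on treatment.

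**The case against.** **Early losses in this cohort are visible elsewhere.** This stands. SAP 2.6.2 reports the Week 48 MMR rate for patients in MMR at baseline, with discontinued or unassessed patients as non-responders, and also molecular response categories by time point for FAS 2. Both classify the PCR value itself. A reader might infer that the plan hides early loss of response altogether; it does not. What remains is a duration curve that can disagree with those tables.

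**The 5-fold limb guards against assay noise, and a FAS patient with a nadir of 0.08% and then 0.3% is not a loss either.** This is fair, and the guard should stay. The difference in FAS 2 is that a lower pre-treatment value exists and is left out. FAS patients cannot have the Week 12 problem, because they enter the duration analysis only after a value at or below 0.1% on study.

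**Baseline might be implied.** Neither document says so, and the SAP 2.1.1 definition of baseline points the other way.

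**The clock may start at first on-study MMR.** SAP 2.6.2 does not say, while SAP 2.1.1 includes FAS 2 efficacy data from baseline. On that reading a patient out of MMR from Week 12 onward has no start date and drops out, which also flatters duration.

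**Changing the definition has knock-on effects.** This stands and limits the remedy. Confirmed loss of MMR is a treatment-failure event (SAP 5.4.4), and FAS 2 efficacy data stop at treatment failure (SAP 2.1.1). A global change in 5.4.1 would alter other summaries.

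**Conclusion.** The point holds as a gap in the FAS 2 duration analysis. As written, a Week 12 loss cannot be counted when Week 12 is the first on-treatment PCR. A later early loss can be missed or dated late when all earlier on-treatment values exceed 0.02%. A patient's recorded duration can be lengthened by this, never shortened.

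Three stronger readings are tempting and not supported:
- That duration in FAS 2 is overstated as a matter of fact. The documents give no early-loss rate; the size is about 3.3 points or more per masked loss with up to 30 patients, and zero if there are none. An unscheduled PCR before Week 12 could also supply a lower reference, and AP/BC progression and CML-related death remain events.
- That duration of MR4 without loss of MMR is biased in the same way. It is exposed only where MR4 was present at baseline and never seen on treatment.
- That other FAS 2 results or the main conclusion are at risk. The Week 48 rate and by-visit categories in FAS 2 do not use the fold-rise, and the primary test and its sample size concern FAS.

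The endpoint is secondary, descriptive and untested. The change is worth making because the error runs in the favourable direction and the correction is cheap.

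**What to change.** In SAP 2.6.2, for the FAS 2 duration-of-MMR and duration-of-MR4 analyses only:
- take the reference for the 5-fold rise as the lower of the baseline value and the lowest on-treatment value, and keep the confirmation requirement;
- include all FAS 2 subjects in the duration-of-MMR analysis, with the clock starting at randomization.

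Leave unchanged the general definition in SAP 5.4.1, the treatment-failure definition in 5.4.4 and the rule for FAS. Record the departure from Protocol 8.3.1.1 in SAP Section 4, which at present lists no changes.

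The cost is small. Protocol 8.1 already requires the central baseline RQ-PCR result before enrolment, so no new data are needed, only SAP text and one derivation. The FAS 2 duration estimate may become slightly less favourable. Rises of less than 5-fold from baseline (for example 0.08% to 0.3%) remain uncounted; an optional sensitivity analysis using any confirmed value above 0.1% would show how much that matters.
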